3.2. DESCRIPTION OF TRIAL DESIGN

Design and Investigational Plan:

This is a multi-center, double-masked, randomized, vehicle-controlled, two cohort study. Subjects will be randomized into either 0.2% AXR-270 Cream (approximately 42 subjects in Cohort 1), 2.0% AXR-270 Cream (approximately 42 subjects in Cohort 2) or Vehicle (approximately 42 subjects) administered in both eyes.

Cohort 1:

Approximately sixty-three (63) subjects with a diagnosis of symptomatic posterior blepharitis associated with MGD meeting all inclusion/exclusion criteria at the Screening visit (Visit 1) will be asked to discontinue their eyelid hygiene regimen and use only Sponsor supplied commercial sterile eyelid wipes between Visit 1 and Visit 2 daily (Equalization Period). Subjects will then be evaluated at Baseline/Randomization (Visit 2; Week 0/Day 1) to confirm they continue to meet all inclusion/exclusion and are eligible for randomization. Note: The use of sponsor-supplied sterile eyelid wipes is to be discontinued after randomization at Visit 2. All subjects within this Cohort will be assessed for safety and exploratory efficacy. Both Investigator and subjects will be masked as to the IP. Subjects will be shown an instructional video on applying the investigational product to help ensure consistency in application across subjects. Further, the site should reinforce to the subject how to self-administer the IP to the eyelids and avoid ocular instillation. Subjects will self-administer a pre-specified volume (approximately 50 milligrams per eyelid) of 0.2% AXR-270 Cream or its Vehicle across the epidermis corresponding to the external surface overlying the tarsal plate of the upper and lower eyelids of both eyes. Refer to more detailed instructions in the Subject Dosing Instructions document. Blood draws for safety labs for all subjects will be performed prior to IP dosing in the clinic at Visit 2/Day 1. Following the in-clinic dose administration, subjects will be supplied with sufficient IP (2 tubes) to apply once daily at home in the evening during the treatment period. Subjects will self-administer IP QD in the evenings beginning on Day 2.

[figure not shown]
On the following week (Visit 3; Week 1/Day 8), the Investigators will examine the subject and perform all safety and efficacy assessments (excluding safety labs and dilated Ophthalmoscopy).

Subjects will return for a Week 2 (Visit 4; Day 15) visit, wherein the Investigators will examine the subject and perform all safety and efficacy assessments (excluding safety labs and dilated Ophthalmoscopy). Subjects will return the used IP and will be instructed to use the 2nd IP tube dispensed at Visit 2 to apply once daily at home in the evening for the remaining 1 week of treatment duration.

Following the completion of the fifteenth (15th) subject from Visit 4 of Cohort 1, the Data Safety Review Committee (DSRC) will meet to review safety data and will make a recommendation about whether to escalate to the higher (2.0%) dose of AXR-270 Cream for Cohort 2, which if recommended, will begin immediately upon completion of enrollment in Cohort 1.

Subjects will return for a Week 3 (Visit 5; Day 22) visit, wherein the Investigators will examine the subject and perform all safety and efficacy assessments (including safety labs). Subjects should not dose at Visit 5/Day 22 and following the visit, subjects will exit the study. Remaining IP will be collected from every subject. (See Appendix 1 for procedures planned for this study).

FIGURE 1: STUDY SCHEMATIC (COHORT 1)

Note: Cohort 2 (AXR-270 2.0% Cream or vehicle) follows the same visit schedule as above and will start enrolling once enrollment of Cohort 1 is complete.

Cohort 2:

Following the completion of the fifteenth subject from Visit 4 of Cohort 1, the DSRC will meet to review safety data and will make a recommendation about whether to escalate to the

higher (2.0%) dose of AXR-270 Cream for Cohort 2, which if recommended, will begin immediately upon completion of enrollment in Cohort 1.

The Screening and study visits will be conducted in the same fashion as described above for Cohort 1. Approximately sixty-three (63) subjects will be randomized to 2.0% AXR-270 Cream or its Vehicle. A study schematic follows (Figure 1).

3.2.1. Investigational Product

The AXR-270 Cream IP is a sterile, water in oil, cream formulation in which micronized AXR-270 Active Pharmaceutical Ingredient (API) is suspended uniformly for topical application to the upper and lower eyelids at either 0.2% or 2.0% concentrations.

The IP is packaged in laminated polyfoil tubes. Each tube will contain 5g of sterile AXR-270 topical cream. Subjects randomized to the Vehicle control arm will receive the same containers containing all components at the concentrations used in the AXR-270 Cream except for the active component.

The product composition is presented in [Table 1](#).

Table 1: Composition of AXR-270 Investigational Product (0.2% and 2.0% Concentrations, Vehicle)

Material	Grade	Function	Vehicle Formula (% w/w)	0.2% AXR-270 Cream Formula (% w/w)	2.0% AXR-270 Cream Formula (% w/w)
White Petrolatum	USP	Vehicle	47.89	47.69	45.89
Emulsifier 10	N/A	Emulsifier	3.30	3.30	3.30
ST- Elastomer 10	N/A	Emulsifier	2.00	2.00	2.00
Mineral Oil	USP	Vehicle	8.00	8.00	8.00
ST- Cyclomethicone 5-NF	NF	Emollient	6.60	6.60	6.60
Propylene Glycol	USP	Solvent	8.00	8.00	8.00
Methylparaben	NF	Preservative	0.08	0.08	0.08
Propylparaben	NF	Preservative	0.02	0.02	0.02

Sterile Water for Irrigation	USP	Vehicle	24.00	24.00	24.00
Anhydrous Citric Acid	USP	Buffer	0.05	0.05	0.05
Dibasic Sodium Phosphate	USP	Buffer	0.06	0.06	0.06

Each randomized, double-masked IP kit contains 3 tubes of IP, each tube sufficient for 2 weeks of dosing.

IP Dispensation Instructions

At Visit 2, randomized subjects will be assigned to an IP Kit which contains three tubes of Double-Masked IP (AXR-270 Cream or Vehicle). The first dose of Double-Masked IP (AXR-270 Cream or Vehicle) will be self-administered by the subject at Visit 2 under supervision of the site staff.

AXR-270 Cream should be stored at 2° to 8°C (36° to 46°F); excursions permitted between 0° and 15°C (32° and 59°F). Transient spikes up to 25°C (77°F) and not to exceed 24 hours are permitted. IP should be protected from light and moisture. The refrigerator will be temperature monitored. IP will be supplied to subjects in coolers with gel packs to maintain refrigerated temperature while in transit.

Timing of Self-Administration

At Visit 2, sufficient training will be provided to the subjects to self-administer their once-daily dose of double-masked IP. Subjects will then self-administer additional doses of IP at home for the remainder of the study. Two tubes of randomized double-masked IP will be dispensed to each subject at Visit 2 for self-administration. The first tube will be used from the time of Visit 2 to the time of Visit 4. The second IP tube will be used from Visit 4 to Visit 5 (note: if a subject is unable to come in to the clinic for Visit 4, they should begin dosing with the second tube on Day 15). One tube from the kit will be kept in reserve at the clinic. Refer to more detailed instructions in the Subject Dosing Instructions document.

3.2.2. Methods to Minimize Bias

To minimize bias, the following measures will be taken:

- IP allocation (AXR-270 Cream versus Vehicle) will be randomized and masked to the Sponsor, subjects, and investigative staff.
- The randomization schedule will be generated by an independent unmasked statistician (who is not on the project team) or designee and maintained in a secure and limited-access location separate from the study Investigator and members of the project team.

4. SELECTION OF SUBJECTS

4.1. SUBJECT INCLUSION CRITERIA

At Visit 1 (and Visit 2 where applicable), individuals of any gender or any race will be eligible for study participation if they:

1. Have provided written informed consent prior to any study procedures.
2. Are 18 years of age or above.
3. Have a clinical diagnosis of moderate to severe MGD and who meet both of the following criteria, in at least one qualifying eyelid (upper and lower eyelid for each eye that will be evaluated independently), at both Visit 1 (Screening) and again in the same eye/eyelid Visit 2 (Randomization) examinations:
 - a) Total MGD score ≥ 5 and ≤ 14 (the sum of secretion 5 central glands on the upper and lower eyelids will be evaluated, each will be scored from 0-3; 0 = clear/slightly yellow, 1 = opaque/yellow, whitish, particulate, 2 = paste, 3 = none/occluded; total score will range from 0-15) and
 - b) Clinical sign severity score of at least 2 (moderate) on vascularity of the eyelid margin
4. Have a score of ≥ 35 in Eye Discomfort VAS (0-100 point scale) at both Visit 1 and Visit 2.
5. Meet the following criteria, in both or the same qualifying eye as in Inclusion #3, at both Visit 1 (Screening) and Visit 2 (Randomization) examinations:
 1. tFCS score ≥ 3 and ≤ 14 (NEI/Industry Workshop scale; 0-15 scale)
 2. Schirmer score of > 7 mm without topical anesthesia
6. OSDI score > 30 at both Visit 1 and Visit 2.
7. Required use of non-prescription (OTC) artificial tear substitute for symptoms of dry eye more than 3 times per day for 3 consecutive days within 30 days prior to the Screening Visit (Visit 1) and willingness to suspend use of tear substitutes at Visit 1 and for the duration of study participation.
8. Are willing and able to follow instructions and willing to be present for the required study visits for the duration of the study.
9. Have a LogMAR BCVA equal to or better than +0.7 using corrective lenses if necessary, in both eyes at both Visit 1 and Visit 2, by Early Treatment of Diabetic Retinopathy Study (ETDRS) or modified ETDRS.
10. If female, are non-pregnant, non-lactating and women of childbearing potential (WOCBP) must be using an acceptable method of birth control [e.g., an Intrauterine Contraceptive Device (IUCD) with a failure rate of $< 1\%$, hormonal contraceptives, or a barrier method] for the duration of the study. If a female subject is currently abstinent, they must agree to use one of the acceptable methods of birth control before they become sexually active.

- A non-childbearing potential is defined as a woman who is postmenopausal for 12 consecutive months or a woman who is post hysterectomy, bilateral oophorectomy or 3 months status post bilateral tubal ligation.

4.2. SUBJECT EXCLUSION CRITERIA

In order for subjects to be eligible at Visit 1 they may not:

1. Have presence or history of iritis/uveitis in either eye.
2. Have lid structural abnormalities including but not limited to entropion or ectropion that in the opinion of the Investigator may confound the study data.
3. In the study eyelid, have greater than 4 glands that are not expressible from the 5 upper and/or 5 lower eyelid meibomian glands at both Visit 1 and Visit 2.
4. Subjects with ocular inflammatory conditions (e.g., conjunctivitis, keratitis, severe anterior blepharitis, etc.) not related to MGD.
5. Subjects who in the study eye have tFCS total score = 15 or a FCS score = 3 in either eye in the superior region NEI/Industry Workshop scale or subjects who have FCS with diffuse confluent staining, filaments or frank epithelial defects at either Visit 1 or Visit 2.
6. Have suspected ocular fungal, viral or bacterial infection.
7. Subjects who within the past 6 months have had cauterization of the punctum. Non-dissolvable plugs must not be inserted within 2 weeks of Screening (Visit 1) and current non-dissolvable plugs in position must be stable in the Investigator's opinion.
8. Use of any of the prohibited medications (see Table 2: List of Prohibited Medications and/or procedures) within a time period prior to or upon Screening (Visit 1). NOTE: These medications may not be used after Visit 1 through the end of the study.

Table 2: List of Prohibited Medications and/or Procedures

Medication	Minimum Washout Period Prior to Screening (Visit 1)
Have had incisional ocular surface surgery (e.g., LASIK, refractive, pterygium removal)	12 months
Penetrating intraocular surgery	90 days
Topical ocular or systemic antibiotics for the treatment of an ocular condition	30 days

Topical cyclosporine	30 days
Lifitegrast	30 days
Systemic corticosteroids (oral, injectable, inhaled, and nasal)	30 days
Topical ocular corticosteroids, ocular non-steroidal anti-inflammatory drugs (NSAIDs), and topical dermatologic corticosteroids on the face within 30 days prior to Visit 1 and during study participation. Topical dermatologic corticosteroids not used on the face are allowed if applied to less than 3 areas for less than 3 consecutive days	30 days
Topical ocular antihistamine and/or mast cell stabilizers within 30 days prior to Visit 1 or during study participation. Have used topical ocular vasoconstrictors for the purpose of eye whitening within 30 days prior to Visit 1 (phenylephrine used to dilate the eyes is allowed)	30 days
Treatments for MGD including but not limited to thermal pulsation (Lipiflow), debridement of lid margin (BlephEx), thermal application (MeiBoFlo, Tear Care), or meibomian gland probing	30 days
All topical ophthalmic gels, ointments or drops (including artificial tears) and the TrueTear [®] Stimulator	2 days
Contact Lenses	At Screening

9. Use short-term dissolvable plugs for 3 months prior to Screening (Visit 1) and long-term dissolvable plugs within 6 months prior to Screening (Visit 1).
10. Any prior use of isotretinoin.
11. Are unwilling to discontinue use of cosmetic makeup applied to the eyelids or eyelashes on the day of a study visit after Visit 1.
12. Have a known hypersensitivity to active ingredient or to any of the other ingredients in the IP.
13. Are unable or unwilling to withhold the use of eyelid scrubs or use of mechanical eyelid cleaning therapy during the study, other than the Sponsor supplied commercial sterile eyelid wipes from Visit 1 through Visit 2. After Visit 2, subjects are also permitted to follow their usual routine to remove eyelid or eyelash makeup (including eyelid wipes), ensuring that no new products/techniques are introduced during the study.
14. Have been diagnosed with glaucoma, are currently using any glaucoma medication or known to have elevated IOP related to steroid use.

15. Have a history of herpetic keratitis.
16. Have a concomitant ocular pathology other than condition under study assessed as potentially confounding by the Investigator.
17. Have a serious systemic disease or uncontrolled medical condition that in the judgment of the Investigator could confound study assessments or limit compliance.
18. Have been exposed to any investigational drug or investigational device within the preceding 30 days.
19. Are an employee of the site that is directly involved in the management, administration, or support of this study or be an immediate family member of the same.
20. Have trigger factors that in the opinion of the Investigator may confound the data, including but not limited to conjunctivochalasis, allergic conjunctivitis, contact lens intolerance, trichiasis, epithelial basement membrane dystrophy, infectious keratitis or conjunctivitis.
21. Have a documented history of ocular allergies, which, in the judgment of the Investigator, are likely to have an acute increase in severity due to the expected timing of the exposure to the allergen to which the subject is sensitive. Subjects sensitive to seasonal allergens that are not expected to be present during the study are permitted.

4.3. STUDY EYE/EYELID

The study eye/eyelid is the eye with the eyelid having the worst (higher) score defined as the sum of the following two severity scores for the clinical signs of MGD:

1. Vascularity of eyelid margin
2. Total MGD Score

If both eyes, and eyelids, have the same score, then select the right eye and upper eyelid.

4.4. RANDOMIZATION

At the Randomization Visit (Visit 2), an eligible subject must continue to meet all clinical inclusion/exclusion criteria as defined in Sections 4.1 and 4.2. Note: Subjects must meet all criteria from Visit 2 eye/eyelid specific criteria in the same qualifying eye and/or qualifying eyelid as in Visit 1.

5. PROCEDURES

Written Informed Consent and Health Insurance Portability and Accountability Act (HIPAA) authorization will be obtained from all subjects prior to any study procedures being performed. Visit assessments will be performed in the order suggested **in both eyes**.

5.1. VISIT DESCRIPTIONS

NOTE: In light of the Coronavirus Disease 2019 (COVID-19) pandemic, the site should utilize risk mitigation techniques for all in-clinic visits as described by the American Academy of Ophthalmology (Appendix 17).

5.1.1. Visit 1 (Screening): Day minus 14 (± 2 days) prior to Visit 2

The following will be performed/assessed in the order suggested below and in both eyes:

- Explain the purpose and conduct of the study to the subject, answer the subject's questions, and obtain written informed consent.
- Obtain information including demographics, concomitant medications, ocular and systemic medical and medication history and surgical history.*
- Evaluate eligibility
- A Screening Identification (ID) should be assigned to the Subject once any Visit 1 procedures (other than ICF) are performed. The Subject ID format will be XXX-001 where XXX represents the site number and the last three digits represent the unique subject number.
- Subject-rated symptom assessments (in this order):
 - Individual Symptom Assessment via VAS
 - OSDI
 - Modified BLISS
- Urine Pregnancy Test (UPT) for all eligible women of childbearing potential. *
- For subjects presenting at Visit 1 or Visit 2 with makeup applied to the eyelids or eyelashes, subjects should use a Sponsor provided lid scrub to remove the makeup. (Subjects may resume using makeup between study visits but not on the day of a study visit). Study specific testing related to the evaluation of the eye and eyelids should start 15 minutes after makeup removal.
- For subjects presenting at any post-randomization visit with makeup applied to the eyelids or eyelashes, the site staff should use the Sponsor provided lid scrub to remove the eyelid makeup. Care should be taken not to aggressively clean the lid

margin with the lid scrub and only to gently remove any remaining makeup from the skin surface.

- BCVA
- Slit-lamp biomicroscopy and external eye exam
- TBUT
- FCS
- Investigator-rated assessment of MGD (in both eyes for upper and lower lids)
 - See Appendix 3. Assessment of Efficacy for full description of Investigator-rated assessments for objective signs of change from baseline
- LGS (at a subset of sites)
- Wait 15-20 minutes after LGS before proceeding
- Unanesthetized Schirmer test
- IOP
- Dilated Ophthalmoscopy
- Determine if the subject is eligible to continue in the study. Do not continue screening any subject who does not meet eligibility requirements. Any subject who does not meet eligibility requirements will be designated as a Screen Failure.
- Instruct the subject to discontinue using all prohibited medications for the remainder of the study.
- If the subject is qualified, a four-week supply of commercial lid wipes will be provided.
- Schedule the subject to return for Visit 2 (Day 1) and remind subjects to bring the remaining lid wipes to Visit 2.

* May be performed at any time during the visit in order to facilitate subject and site schedules.

5.1.2. Visit 2 (Randomization): Day 1

Visit 2 will occur 14 (± 2 days) after Visit 1 (Screening). The following will be performed/assessed in both eyes:

- Evaluate continued eligibility
- Subject-rated symptom assessments (in this order):
 - Individual symptom assessment via VAS
 - OSDI
 - Modified BLISS
- Use of any concomitant medications since the last visit

- Occurrence of any AEs since the last visit
- BCVA
- Slit-lamp biomicroscopy and external eye exam
- TBUT
- FCS
- Investigator-rated assessment of signs of MGD
 - See Appendix 3. Assessment of Efficacy for full description of Investigator-rated assessments for objective signs of change from baseline
- LGS (at a subset of sites)
- Wait 15-20 minutes after LGS before proceeding
- Unanesthetized Schirmer test
- IOP
- Safety laboratory blood draw
- Determine if subject is eligible for randomization

For eligible subjects, the following is the process regarding administration of Double-Masked IP whereby the trained site staff will conduct the following procedures:

- Enter subject information into IWRS to determine randomization code and Kit Number. Cohort 1 versus Cohort 2 will be part of the Interactive Web Response System (IWRS) input
- Show the subjects an instructional video on applying the investigational product. Review Subject Dosing Instructions document, reiterating that the subject should administer IP across the entire surface (corresponding to the tarsal plate) of the upper and lower eyelids of both eyes
- Subject will self-administer first dose of double-masked IP in clinic under the supervision of site staff. The site staff will record the Day 1 dosing time in the source document.
- Assess for occurrence of any IP related AEs
- The subject will complete the IP Comfort Assessment in the clinic approximately 2 minutes following administration. Site will document in the source document.
- Dispense three Daily Dosing Diaries (including IP Comfort Assessment) to the subject. *Note: each diary will contain sufficient entries for approximately one week of dosing*
- Instruct subject to bring completed diaries, cooler/gel packs and used/unused IP to each subsequent clinic visit

- Dispense two tubes of IP to the subject and instruct the subject to open only one tube initially and apply once daily at home in the evening beginning on Day 2
- Dispense a cooler and gel packs to the subject for the purpose of transporting IP. Remind the subject to store the IP and the gel packs in the refrigerator at home and to use the cooler/refrigerated gel packs any time IP is transported including to/from study visits
- Reinforce the subject instructions to administer IP across the entire surface of the upper and lower eyelids of both eyes QD and to record each administration and IP Comfort Assessment on the daily dosing diary
- **Remind subjects to discontinue the use of eyelid wipes for the remainder of the study except if used for routine makeup removal.** Collect Sponsor-provided eyelid wipes from the subject
- Schedule the subject to return for Visit 3 (Day 8 \pm 2 days)

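### No urine pregnancy test is scheduled at Visit 2, where eligibility is rechecked before randomisation and first dose, so the latest scheduled result is 12-16 days old

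*Protocol*

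**What the plan says.** **Eligibility at Visit 2.** Protocol 3.2 has subjects evaluated at Visit 2 "to confirm they continue to meet all inclusion/exclusion and are eligible for randomization". Protocol 4.4 says that at this visit "an eligible subject must continue to meet all clinical inclusion/exclusion criteria as defined in Sections 4.1 and 4.2". The Visit 2 list in 5.1.2 opens with "Evaluate continued eligibility" and, after the examinations, has the site "Determine if subject is eligible for randomization". It then goes on to "Enter subject information into IWRS to determine randomization code and Kit Number", and the first supervised dose is taken in the clinic. Appendix 1 and SAP Table 1 both mark the inclusion/exclusion row at Visits 1 and 2.

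**The criterion.** Section 4.1 opens: "At Visit 1 (and Visit 2 where applicable), individuals of any gender or any race will be eligible for study participation if they". Criterion 10 reads in part: "If female, are non-pregnant, non-lactating and women of childbearing potential (WOCBP) must be using an acceptable method of birth control". It requires contraception during the study.

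**The tests.** A UPT is listed at Visit 1 (5.1.1), Visit 5 (5.1.5) and Early Termination (5.1.7). The lists for Visits 2, 3 and 4 have none. The UPT row in Appendix 1 and SAP Table 1 is marked only at Visits 1 and 5. The one laboratory step written into 5.1.2 is "Safety laboratory blood draw", while 3.1.1 defines the safety labs as including urinalysis.

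**The concern.** Visit 2 is the last point at which exposure of a pregnant subject can be avoided altogether. The other inclusion criteria that rest on a scheduled measurement (Total MGD score, lid-margin vascularity, Eye Discomfort VAS, corneal staining, Schirmer, OSDI and visual acuity) are all measured again at Visit 2. Criterion 10 is the only one with its own scheduled test that is not repeated.

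The contraception rule covers the duration of the study and sets no period before Visit 1. A conception shortly before Visit 1 would therefore breach no rule. It could be too early to show on the Visit 1 strip and become detectable before the first dose. A pregnancy could also begin between the two visits despite contraception.

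For a completer, no scheduled test falls during dosing, so none can prompt withdrawal for pregnancy under 5.2, item 4, while exposure could still be cut short. A positive result at Visit 5 would also leave open whether the subject was already pregnant at randomisation.

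What is at stake is subject safety and the quality of one eligibility check in a Phase I/II trial.

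**Working it through.** The plan states no figure for the age of the test result, so there is none to reproduce. The check is a comparison of the visit lists plus simple interval arithmetic.

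**Inputs**
- Visit 1 to Visit 2: 14 ± 2 days (Protocol 5.1.2).
- Visit 2 is Day 1, with first dose at that visit (5.1.2).
- Visit 5: Day 22 ± 3, that is Day 19 to Day 25 (5.1.5). No dose is taken at Visit 5 (3.2).

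**Where a UPT is scheduled**

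| Visit | UPT listed |
|---|---|
| Visit 1 | yes |
| Visit 2 (randomisation, first dose) | no |
| Visits 3 and 4 | no |
| Visit 5 | yes |
| Early Termination | yes |

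**Age of the latest scheduled result at first dose**
- Now: 14 − 2 = 12 days to 14 + 2 = 16 days.
- Cross-check: SAP Table 2 puts Visit 1 at Day −16 to Day −12 and Visit 2 at Day 1. With no Day 0, that is again 12 to 16 days.
- With a Visit 2 test before dosing: 0 days.

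**Gap between the last pre-dose test and the Visit 5 test, for completers**
- Visit 2 to Visit 5: 19 − 1 = 18 days to 25 − 1 = 24 days.
- Now: 12 + 18 = 30 days to 16 + 24 = 40 days.
- With a Visit 2 test: 18 to 24 days.

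**Early leavers.** For a subject who has the Early Termination visit t days after Visit 2, the gap is t + 12 to t + 16 days now and t days with a Visit 2 test.

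The gain is the same 12 to 16 days in each case, which is simply the interval between Visits 1 and 2. These figures measure the age of a test result. They do not count pregnancies or exposures avoided.

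**The case against.** The strongest reply is that the protocol already covers pregnancy by other means. There is a UPT at screening, and women of childbearing potential must be using contraception as a condition of entry. Eligibility is considered twice at Visit 2, so a site can ask or run an unscheduled test. Pregnancy during participation is a listed ground for discontinuation, with outcome information requested (5.2). All of this stands, and it narrows the gap to pregnancies that the Visit 1 strip misses, or that begin after it, and that are detectable by Visit 2.

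A reader might infer that the protocol contradicts itself by requiring a check that it does not schedule. The documents do not support that. Section 4.1 applies its criteria at Visit 2 only where applicable. Criteria 3, 4, 5, 6 and 9 name both visits and criterion 10 does not. Section 4.4 speaks of clinical criteria, and its note concerns the eye and eyelid. Section 3.2 is broad enough that including criterion 10 is the natural reading, but how it is verified is left open.

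A reader might also infer from the blood-draw wording in 5.1.2 that no urine is collected at Visit 2. That is not established either. The safety labs are defined to include urinalysis (3.1.1; SAP 2.5.3), and Appendix 1 marks the safety lab draw at Visit 2. The SAP tables and listings cover only chemistry and hematology, so collection is uncertain. Urinalysis is in any case not a pregnancy test.

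Finally, the benefit cannot be sized. The documents give no reproductive-toxicity figure, no systemic-exposure figure and no number of women of childbearing potential. They refer to the Investigator's Brochure for toxicology, which could make the gap matter more or less. This limits how strongly the point can be put, but at this cost it is no reason to leave the test out.

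**Conclusion.** The point holds as a low-cost improvement to subject safety. At the visit where eligibility is rechecked and the first dose is given, the plan relies on a scheduled pregnancy result that is 12-16 days old, together with questioning or an unscheduled test. For completers the next scheduled result comes 30-40 days after the screening test, once dosing has ended.

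The conclusion rests on the visit windows being kept and on reading Sections 3.2 and 4.4 as taking in criterion 10. That the test is missing from the Visit 2 schedule depends on neither.

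It would be a mistake to read this as evidence that pregnant women will be exposed or harmed, or that any result is compromised. UPT data are only listed (SAP 4.8.7), and no endpoint, analysis, power or error rate is affected.

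**What to change.** In Protocol 5.1.2, add a UPT for women of childbearing potential, with a negative result required, after the opening eligibility step and before IWRS entry. Mark the UPT row at Visit 2 in Appendix 1 and in SAP Table 1. Keep the tests at Visit 1, Visit 5 and Early Termination.

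The cost is one strip per woman of childbearing potential, of a type already in the protocol, at a visit already attended. The upper bound is about 126 strips if every randomised subject were of childbearing potential, plus any for subjects who fail at Visit 2. If urine is already collected for urinalysis, the strip can use that sample; if not, a sample is added. The downside is an occasional extra screen failure at Visit 2, which is the check doing its job.

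The change has limits. A pregnancy too recent to show at Visit 2 would still be missed, so a positive Visit 5 or Early Termination test becomes less ambiguous but not fully clear. It also adds no result during treatment.
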